home in a naturalistic setting: Week 1-Session 1, WP smokers will smoke using 1 quick-light charcoal and room temperature water in the WP jar, Week 2-Session 2, WP smokers will smoke using 1 quick-light charcoal but adding ice cubes to the water in the WP jar, Week 3-Training for session 3, RAs will train participants on how to use a charcoal-free electrically heated WP head to heat the tobacco, and Week 4-Session 3, WP smokers will smoke WP tobacco without charcoal using the electric WP head and room temperature water. We will collect a) Tobacco Use History; b) 4-week Tobacco Use and Exposure Diaries; c) WP Smoking Session Day and Exposure Form; d) CO exposure: Micro+Smokerlyzer® CO monitor will be used for exhaled CO two minutes pre and post each smoking session; and e) 6 first morning urine samples: pre and post the 3 sessions to measure urinary cotinine, NNAL, 1-HOP, and SPMA. We will measure urinary Furan-BDA-NAL in WP smokers who smoke WP tobacco as commonly practiced using quick-light charcoal and room temperature water in the WP jar (urine samples from Session1).

Inclusion Criteria for Participants

Adult waterpipe smoker: A male or female, 18 years or older, who smokes WP tobacco exclusively, smokes at least 1 WP head per month, and smokes at least 1 WP head per WP smoking session, smokes WP at home, agrees to smoke *Starbuzz* WP tobacco, and lives in a 'smoker home'. Adult non-smoker: A male or female, 18 years or older, who lives in a 'non-smoker home'.

Inclusion Criteria for Homes

A Smoker Home: is a home in which residents have smoked WP tobacco exclusively indoors/outdoors at least in the last month. A Non-smoker Home: is a home where to the knowledge of the residents no smokers have lived in and no visitors had smoked indoors/outdoors in the past month, and where a potential nonsmoker participant who has not been exposed to any secondhand smoke at least in the last month resided full-time.

Exclusion Criteria

Adults with major physical/psychiatric illnesses that are judged by the research assistants (RAs) to interfere with ability to give informed consent or to successfully complete an interview will not be included in the study. Daily WP smokers will be excluded because they may not be able to adhere to the wash-out periods before the 3 WP sessions. Pregnant women are also excluded.

Screening Potential Participants

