Furan is oxidized to a reactive α , β -unsaturated dialdehyde, *cis*-2-butene-1,4-dial (BDA), a toxic metabolite of this liver toxicant and carcinogen. It has been determined that there is a strong relationship between Furan-BDA-NAL and smoking. Levels of urinary Furan-BDA-NAL, a BDA derived metabolite of furan, were higher in cigarette smokers relative to those in nonsmokers. We will measure sulfides 2 and 4; sulfoxides 3 and 5 and BDA-NAL: 1 and 6. In small sample sizes (N=5, N=16), furan metabolite sulfoxide 3 ranged from 8.7 to 69 pmol/mg creatinine among cigarette smokers and from 1.4 to 6.5 pmol/mg creatinine, with LOQ of <.02. We will be the first to determine the levels of Furan-BDA-NAL in WP smokers, thereby assessing WP smokers' potential health risks associated with furan exposure.

Laboratory Analyses for the Proposed Urinary Biomarkers.

Dr. [name] laboratory at The Masonic Cancer Center, University of Minnesota, will conduct the following laboratory urine analyses, as described previously: NNAL with a LOQ of 1.672 pg/mL (0.01 pmol/mL), 1-HOP with a LOQ of (0.05 pmol/mL), SPMA with a LOQ of 0.03 pmol/mL, Furan-BDA-NAL with a LOQ of <.02 pmol/mg creatinine). [name] at SDSU will conduct laboratory urine analyses for cotinine with a LOQ of 0.1 ng as described previously; and will conduct laboratory analyses for creatinine for normalization.

Gender Representation. Efforts will be made to recruit equal samples of males and females.

Participants Retention and Incentives. Flexible scheduling for study activities where applicable. Following completion of study activities, a \$75 check issued by SDSU will be mailed to non-smokers, and \$250 to smokers: \$100/smoking session and \$25/ training session. Proration will apply for completed activities.

Study Timeline. (Table 3) In the first 3 quarters of Year 1 we will develop forms and procedure manuals, hire and train staff, pilot test and refine protocols and study measures, and obtain IRB approval. Sequential recruitment of participants, data collection, urine aliquoting, data entry, cleaning and coding will start during the 4th quarter of Year 1, and continue through the end of year 2. We expect we will need about 15 months to complete data collection in naturalistic settings. Data analysis and manuscript preparation will start in year 3. Dissemination of results will start in Year 3.

Table 3. Timeline	1			2	3
Forms Procedures manual development					
Hire and train staff					

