IRB approval, pilot testing of data					
collection					
Refine data collection & procedures					
manual					
Recruitment of participants					
Measures:					
Study Questionnaire, Forms & Diaries					
CO concentrations, Urine samples					
Battelle - Laboratory analyses					
Urine aliquoting, shipping samples to labs					
Data processing-coding, entry, cleaning					
Data analysis and manuscript preparation					
Dissemination of Results (continues beyond year		⁻ 3)			

General Statistical Analysis Strategy. [name] will oversee data processing and. Statistical analyses will be determined by Drs. [name], [name], [name], [name] and [name]. Final analyses will be conducted using SPSS and Stata software by [name], [name], and [name]. Type I error rate will be set at α =.05, and corrections for Type I error will be performed as necessary (e.g., Bonferroni). We will begin with a comprehensive descriptive analysis of levels of toxicants, CO, and urinary biomarkers and their distribution in the various smoking configurations. Arithmetic means and standard deviations, geometric means and 95% confidence intervals, medians and 25th and 75th percentiles, and minimum and maximum levels will be computed for each outcome measure, and for uncorrected and creatinine-corrected values of urinary biomarkers. Correlations between biomarkers will be determined by Pearson's r. Measures will be log-transformed as necessary, to control for skewed distribution, the undue influence of outliers, and violations of assumptions for statistical inference. Dependent or independent samples t-tests, as appropriate, will compare pairs of machine smoking configurations, smokers post-session vs. pre-session, and smokers vs. non-smokers. Missing data from the questionnaire will be handled using multiple imputation in Stata.

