Aim 1 calls for comparing pre/post session change in exhaled CO, and in urinary levels of cotinine, NNAL, SPMA, and 1-HOP in first morning urine samples the morning of, and the morning after, each of 3 WP smoking sessions at home: (Session 1) using charcoal to heat the tobacco and only water in the jar; (Session 2) using charcoal to heat the tobacco and adding ice cubes in the jar; and (Session 3) using electrically heated tobacco and only water in the jar. Among smokers, differences in pre/post change on CO and each biomarker between sessions 1 & 2, and between sessions 1 & 3, will be assessed by mixed regression models to handle repeated measures on each participant. Demographics, duration of smoking, and possible confounding factors, such as number of smokers inside the home and years smoked, will be included as covariates.

Power analysis. As no data exist on effect sizes of differences between session configurations for Aim 2, in Table 4 we show estimated power to detect difference for a range of potential intra-class correlations (ICC) and an effect size of .40 (medium by Cohen's criteria), based on paired z-test, n=50, two-sided alpha=.05. Estimates are conservative, since addition of covariates and adjustment for pre-session CO or urinary biomarker levels in the analyses will increase power.

Table 4. Power				
estimate	es			
Effect	ICC	Darran		
Size	icc	Power		
0.40	0.25	0.637		
0.40	0.50	0.807		
0.40	0.75	0.979		

Aim 2 will examine levels of urinary Furan-BDA-NAL following the analysis strategy described in Aim 1, but using data only from Session 1, the configuration commonly practiced in naturalistic settings, using charcoal to heat the tobacco, and room temperature water in the jar. We will begin with a comprehensive descriptive analysis of demographics and Furan-BDA-NAL levels and their distribution in WP smoker participants. As in Aim 1, analyses will identify differences in metabolite levels between smokers vs. non-smokers, and between pre vs. post WP smoking Session 1, for the sample overall as well as by demographic categories (age, gender, BMI). Pearson's correlations will be conducted between urinary levels of Furan-BDA-NAL and values of other metabolites (cotinine, NNAL, SPMA, and 1-HOP) quantified for WP smoking Session 1.

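### Plain Pearson correlations between metabolites from the same urine void can show association that comes only from shared dilution or shared creatinine; partial out log creatinine, with one row per smoker

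*Combined protocol and SAP*

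**What the plan says.** - **General Statistical Analysis Strategy:** "Correlations between biomarkers will be determined by Pearson's r". Descriptive statistics are planned "for uncorrected and creatinine-corrected values of urinary biomarkers", but no scale is named for the correlations. On transformation: "Measures will be log-transformed as necessary, to control for skewed distribution".
- **Aim 2:** Pearson's "correlations will be conducted between urinary levels of Furan-BDA-NAL and values of other metabolites", namely cotinine, NNAL, SPMA and 1-HOP, as "quantified for WP smoking Session 1".
- **Study Design and Target Population:** each smoker gives "6 first morning urine samples: pre and post the 3 sessions", so Session 1 yields two voids per smoker. Aim 2 does not say whether the correlations use the pre value, the post value, both or the change.
- **Laboratory Analyses for the Proposed Urinary Biomarkers:** one laboratory "will conduct laboratory analyses for creatinine for normalization". The furan quantification limit is given per mg creatinine. The biomarker sections also quote earlier cotinine, NNAL, SPMA and furan values per mg creatinine.

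The plan gives no creatinine adjustment, partial correlation or repeated-sample method for the correlations. The mixed models for repeated measures are described under Aim 1, for pre/post change.

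**The concern.** Two concentrations from one void rise and fall together with its dilution. If both are divided by the same creatinine value, dilution cancels, but person-to-person variation in creatinine excretion then enters both with the same sign. Either way the two values have a positive covariance that says nothing about a common source. On the log scale the shared factor becomes a shared additive term, so the permitted log transformation leaves it in place. A Bonferroni correction does not help either, because the expected r under no association is no longer zero.

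The protocol notes that furan also comes from processed food, pollution and car exhaust, and that furan metabolite levels have not been determined before in waterpipe smokers. A positive correlation with tobacco biomarkers would be easy to read as support for a smoke source, and there are no earlier waterpipe data to check it against.

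**Working it through.** **The plan's own figure.** Table 4 is the only computed design figure. With power = Φ(0.40·√50/√(2(1−ICC)) − 1.96), ICC 0.25, 0.50 and 0.75 give 0.637, 0.807 and 0.979, as printed. It concerns session differences. No figure is given for the correlations.

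**Inputs from the documents**
- n = 50 smokers and two-sided α = 0.05, so the critical |r| is 0.279.
- Log-SD from a geometric-mean interval is ln(upper/lower)/(2×1.96)×√n.
  - Cotinine before smoking: ln(19.2/7.21)/3.92×√55 = 1.85.
  - SPMA after smoking: ln(0.83/0.40)/3.92×√50 = 1.32.
  - SPMA before smoking: ln(0.41/0.17)/3.92×√50 = 1.59.
- Furan has only ranges, in samples of 5 and 16 whose assignment is unclear. The range 8.7–69 implies a log-SD of about 0.59 (if N=16) to 0.89 (if N=5). The range 1.4–6.5 implies 0.44 to 0.66.

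**Assumed, because the documents do not give them**
- Log-SD of dilution, d: 0.4–0.8.
- Log-SD of creatinine excretion, e: 0.2–0.4.
- Log-SD of furan, s₁: 0.5–0.9.
- s₂ is 1.3 (SPMA) or 1.85 (cotinine). s₁ and s₂ are treated as each metabolite's own variation.

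**Model.** Log furan = F + D, log comparator = X + D and log creatinine = D + E, with F, X, D and E independent. The metabolites are therefore truly unrelated. The spurious correlation is r = k/√((s₁²+k)(s₂²+k)), where the shared covariance k is:
- uncorrected: k = d²
- creatinine-corrected: k = e²
- partial, given log creatinine: k = d²e²/(d²+e²), which is below both d² and e²

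Because r increases with k, the partial correlation has the smallest spurious r in every setting. The false-positive rate is close to Φ(√(n−3)·atanh r − 1.96) plus the negligible or small opposite tail, with n−4 for the partial correlation. Simulation (20,000 runs per setting) agrees within about one percentage point.

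**Middle setting** (d = 0.6, e = 0.3, s₁ = 0.6), with SPMA:
- Uncorrected: 0.36/√(0.72×2.05) = 0.296
- Corrected: 0.09/√(0.45×1.78) = 0.101
- Partial: k = 0.36×0.09/0.45 = 0.072, and 0.072/√(0.432×1.762) = 0.083

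| Comparator | Uncorrected: r, false positives | Corrected: r, false positives | Partial: r, false positives |
|---|---|---|---|
| SPMA | 0.296, 56% | 0.101, 11% | 0.083, 9% |
| Cotinine | 0.218, 34% | 0.072, 8% | 0.059, 7% |

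**Extremes over all settings**

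| Method | Smallest r, false positives | Largest r, false positives |
|---|---|---|
| Uncorrected | 0.16/√(0.97×3.58) = 0.086, 9% | 0.64/√(0.89×2.33) = 0.444, about 92% |
| Corrected | 0.04/√(0.85×3.46) = 0.023, 5% | 0.16/√(0.41×1.85) = 0.184, 25% |
| Partial | 0.032/√(0.842×3.454) = 0.019, 5% | 0.128/√(0.378×1.818) = 0.154, 18% |

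The low ends use cotinine and s₁ = 0.9. The high ends use SPMA and s₁ = 0.5.

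**The case against.** - **The correlations are secondary.** A reader might infer that they are Aim 2's evidence that furan tracks waterpipe smoke. The documents do not say so. Aim 2 names the smoker versus non-smoker and pre versus post comparisons first, and the stated expectation is only a post-smoking increase. The correlations come in a closing sentence with no hypothesis, power or decision rule. This stands, and it limits what is at stake.
- **Pooling is not planned.** A reader might infer that pre and post values will be stacked as 100 independent rows. The plan does not say this, and separate pre and post correlations fit its text. If stacking were done, ignoring the pairing alone would give about 8% false positives at a within-person correlation of 0.5 and 13% at 0.8. Any further inflation because both markers rise after the session reflects real shared exposure, not an artefact of this kind. What stands is that the time point should be stated.
- **The bias may be small.** The documents give no creatinine or dilution SD. If corrected values are used and creatinine mainly tracks dilution, r is often well below 0.279. Using the pre-smoking SPMA log-SD of 1.59 would shrink r further. The 92% figure is a corner in which dilution supplies 0.64/0.89 = 72% of the variance in log furan. All of this stands.
- **The remedy gains little over corrected values.** The gain is modest in many settings (11% to 9% in the middle case for SPMA). It is larger for uncorrected values, which the plan does not exclude, and in no setting does the partial correlation have a larger expected bias than either plain version.

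**Conclusion.** The point holds as a weakness in a secondary, descriptive analysis. Plain Pearson's r on metabolites from the same void is open to spurious positive correlation on either scale, and nothing in the plan removes it. Under the stated assumptions the false-positive rate at n=50 is about 9–92% for uncorrected values and 5–25% for corrected values. The direction follows from the design. The size rests on assumed SDs for dilution, creatinine excretion and furan.

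The documents do not support the stronger statement that unrelated metabolites will appear correlated. In many settings the expected r is below the critical value, and for corrected values it is below it in all settings examined. Aim 2's group and pre/post comparisons, Aim 1 and Table 4 do not depend on this.

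**What to change.** In Aim 2, and in the general rule for correlations among urinary biomarkers, replace plain Pearson's r with the partial correlation of log uncorrected concentrations given log creatinine. Compute it separately for the pre and the post void, so that each smoker contributes one row, and state the scale and time point in the text. Report that the adjustment lowers the artefact but may leave some of it (about 5–18% false positives in the settings above).

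The correlation of within-person log changes (post minus pre), given the change in log creatinine, may be added as a supportive analysis. It need not become the main one.

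Cost: SAP wording, a few lines of code and one degree of freedom per correlation. Some reported correlations will be smaller. Creatinine is already being measured, so no new samples or assays are needed.
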